Introduction: Glycemic control in acutely ill stroke patients with hyperglycemia is vital. Although insulin is the choice of anti-diabetic agent during acute stage, it is not clear which insulin regimen is better in terms of glycemic control and prevention of hypoglycemia in hospitalized acute stroke patients who are usually on small frequent nasogastric tube feeding. The present study aims to evaluate the efficacy and safety of human insulin (regular insulin and neutral protamine hagedorn, NPH insulin) to analog insulin (basal insulin glargine and rapid acting insulin aspart) in hospitalized acute stroke patients with hyperglycemia.

Justification: Analog insulins are developed by minor alteration of the amino acid chain which alters their pharmacokinetics and make them more physiological. However, these insulins are costly and are not widely available. Conventional human insulins are more commonly used in our country. Comparison of these two regimen is necessary in our own setting to optimize optimal glycemic management of hospitalized acute stroke patients.

Methodology: In this single-center, open-label, randomized trial, 100 patients with acute stroke and hyperglycemia (capillary blood glucose ≥ 10 mmol/L on 2 or more occasions) or history of type 2 DM admitted in the in-patient Department of Neurology, National Institute of Neurosciences (NINS) & Hospital will be randomly assigned to receive human insulin or modern insulin therapy in 1:1 ratio. The study will be carried out from February to June 2021. Blood glucose (BG) will be monitored by standardized glucometer thrice a day and insulin dose will be adjusted daily. The primary outcome of the study will be the differences in glycemic control between groups, as measured by mean daily BG concentration during the hospital stay. Secondary outcomes include differences between treatment groups in any of the following measures: number of hypoglycemic events (BG < 3.9 mmol/L), total daily dose of insulin, length of hospital stay, hospital complications and mortality.

Expected outcome/ result: The result will clearly show the efficacy and safety of newer insulins in comparison to conventional human insulin.

Recommendation: The study may help generating recommendations about insulin use in hospitalized acute stroke patients.

Section-C

INTRODUCTION:

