It is well known that good clinical outcome in hospitalized patients with hyperglycemia cannot be expected unless target blood glucose is promptly achieved and maintained (1-3). This is also true for acute stroke patients. Hyperglycemia may affect the outcome of both ischemic and hemorrhagic stroke (4-6). Pro-oxidative and proinflammatory state imposed by hyperglycemia can cause direct neuronal toxicity. An increase of cerebral edema may be caused by hyperglycemia-mediated increase in matrix metalloproteinase-9 causing neuronal damage. Moreover, hyperglycemia may be responsible for a procoagulant state that can further compromise blood supply to the penumbral areas in acute ischemic stroke (7).

Management of hyperglycemia in acute stroke patients is particularly challenging because many of the patients cannot take their usual food and need feeding by nasogastric (NG) tube. Common practice is to feed 200 ml of liquid food (soup or milk) 2 hourly starting at morning and continue up to night (10 feeds/day). As such, insulin regimen used to control hyperglycemia in patients taking three major meals may not be appropriate in this setting. Moreover, many acute stroke patients receive corticosteroid therapy, which further deteriorates glycemic status. Dislodgement of NG tube may result in interruption of interruption of feeding, predisposing to hypoglycemia. All these challenges need to be kept in mind while choosing appropriate insulin regimen.

Hyperglycemia in hospitalized patients is defined as blood glucose levels >7.8 mmol/L. Insulin therapy should be initiated for treatment of persistent hyperglycemia starting at a threshold ≥ 10.0 mmol/L. Once insulin therapy is started, a target glucose range of 7.8–10.0 mmol/L is recommended for the majority of critically and non-critically ill patients (8). More stringent goals, such as <7.8 mmol/L may be appropriate for selected patients, as long as this can be achieved without significant hypoglycemia.

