In different countries, basal-bolus therapies with insulin analogs are being used more commonly. But intermediate-acting and regular human insulin are also observed to have almost similar efficacy and safety (12,14). No inpatient trials have been conducted in our region to determine optimal treatment regimens for hospitalized patients with T2DM in special situation like acute stroke. As there are significant differences in patient demographics, admission cause, feeding practice and availability of hospital resources between patients of developed and developing countries, the choice of agents may not be similar (15,16). In this background, the present study aims to compare the efficacy and safety of conventional human insulin (regular insulin and intermediate acting NPH insulin) to newer analog insulin (basal insulin glargine with rapid acting insulin aspart) in acute stroke patients with hyperglycemia admitted in a referral tertiary neuroscience institute of Dhaka.

RATIONALE:

One in five patients hospitalized for acute stroke has hyperglycemia. For optimum outcome of these patients, proper glycemic control is essential. Acute stroke patients, who need hospitalization, are usually unable to take food normally and they are fed through nasogastric tube with small frequent feeding (200 ml, 2-hourly, 10 feed/day). It is not clear which insulin regimen will suit better to these type of feeding practice. Moreover, corticosteroids (dexamethasone) are often used in these patients as treatment adjunct which further challenges glucose homeostasis. Different insulin regimens are used in such patients but none is validated in clinical trials. Episodes of hypoglycemia may cause further neurological deterioration in acute stroke patients. So regimen with less chance of hypoglycemia needs to be identified. Although analog insulins are observed to have less chance of hypoglycemia, they are costly and had not been well studied in our setting. It is essential for us to know the efficacy and safety of analog insulin regimen in comparison to human insulin, so that appropriate management decision can be made

OBJECTIVES:

General objective:

- To compare the efficacy and safety of human insulin (regular insulin and intermediate acting NPH insulin) to analog insulin (basal insulin glargine and rapid acting insulin aspart) in hospitalized acute stroke patients with hyperglycemia

Specific objectives:

In hospitalized acute stroke patients with hyperglycemia -

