For a patient who is known to have diabetes but were not getting insulin previously (or previous insulin dosage is not known), insulin therapy will be started at a total daily dose of 0.3-0.4 units/kg/day for an admission BG between 10-15 mmol/L or 0.5-0.6 units/kg/day for a BG >15 mmol/L. In previously insulin treated patients, ongoing total daily dose of insulin will be started. If there is history of poor glycemic control with ongoing insulin dose, then 10-20% increase of daily dose of insulin will be considered.

For a patient who is not known to have diabetes, insulin therapy will be started if admission BG is >10 mmol/L in two or more occasions. A total daily dose of 0.3-0.4 units/kg/day will be started if admission BG is 10-15 mmol/L and 0.5-0.6 units/kg/day for a BG >15 mmol/L.

Patients treated with human insulin regimen will receive 50% of total daily dose as NPH insulin at around 6 am and 6 pm, while the rest 50% regular human insulin three times a day in 3 equally divided doses at around 6 am, 12 pm and 6 pm.

Patients treated with modern insulin regimen will receive 50% of total daily dose as basal insulin glargine at the same time of day and 50% as insulin aspart given in 3 equally divided doses at 6 am, 12 pm and 6 pm.

In both groups, insulin dosage will be adjusted daily to a target fasting and premeal BG 7.8-10.0 mmol/L in the absence of hypoglycemia. Insulin dosage will be adjusted daily according to BG values. If the fasting and/or premeal BG is 10-15 mmol/L in the absence of hypoglycemia, the total daily dose will be increased by 10% every day. If the fasting and/or premeal BG is >15 mmol/L, the insulin daily dose will be increased by 20% every day. If a patient develops hypoglycemia (BG <3.9 mmol/L), the insulin daily dose will be decreased by 20%. Supplemental regular insulin will be given in addition to scheduled mealtime insulin for BG >10 mmol/L using a supplemental insulin protocol.

BG will be measured before each bolus insulin injection (at 6 am, 12 pm and 6 pm). Glycated hemoglobin (HbA1c) will be measured after hospital admission if not done within last three months.

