Except anti-diabetic treatment, other treatments will be continued as per the decisions of the treating physicians. If NG feeding is discontinued and patient is kept NPO, conventional group will receive neutralizing insulin with any dextrose containing fluid along with low dose NPH insulin, if needed. Modern insulin group will receive neutralizing insulin with any dextrose containing fluid with glargine insulin as before.

After recruitment, each recruited patient will be visited daily (even in holidays according to a predefined schedule) by one of the investigators and insulin dose will be adjusted according to glucose profile of previous day. Insulin injection and capillary blood glucose monitoring by glucometer will be done by trained nurses as part of their routine patient care. Doctors and nurses on duty will be provided with cell number of the investigators who will receive call on 24/7 basis for any emergency or uncertainty regarding management of hyperglycemia.

Hypoglycemia is regarded as the only short-term adverse event of insulin. As both treatment arms will use established and recognized insulin regimen, no compensation will be provided to the patient or his/her attendants in case of any adverse event. As most of the hospitalized patients have severe stroke with case fatality rate around 20%, death will not be regarded as parameter of primary treatment outcome.

During discharge, last in-hospital insulin dose will be continued with education to the caregiver regarding insulin injection and glucose monitoring technique. No follow up visit is included in the study.

Protocol deviation and protocol violation:

Deviation to protocol will be recorded and reported to ethical committee as soon as possible. Failure to obtain informed written consent, use of incorrect insulin regimen, not fulfilling inclusion and exclusion criteria will be regarded as protocol violation and will be reported to ethical committee immediately. In case of protocol violation, the data of related participant will be discarded.

Outcome variables

The primary efficacy outcome of the study will be the differences in glycemetic control between groups, as measured by mean daily BG concentration during the hospital stay.

The primary safety outcome will be the frequency of hypoglycemic events (BG <3.9 mmol/L).

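### The NPO rule continues basal insulin but adds no glucose check between 6 pm and 6 am, so overnight hypoglycemia can be found late or not counted

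*Combined protocol and SAP*

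**What the plan says.** All references are to the combined protocol and SAP, mostly to Section-C.

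- **BG schedule (Methodology, Study Procedure).** "BG will be measured before each bolus insulin injection (at 6 am, 12 pm and 6 pm"). The Methodology paragraph of the opening summary agrees: "Blood glucose (BG) will be monitored by standardized glucometer thrice a day".
- **NPO rule (Study Procedure).** In the human insulin arm, "conventional group will receive neutralizing insulin with any dextrose containing fluid along with low dose NPH insulin, if needed". In the analog arm, "Modern insulin group will receive neutralizing insulin with any dextrose containing fluid with glargine insulin as before". Neither sentence lists a scheduled bolus or a BG measurement. Glargine is 50% of the total daily dose under the ordinary regimen.
- **Dose reduction (Study Procedure).** "If a patient develops hypoglycemia (BG <3.9 mmol/L), the insulin daily dose will be decreased by 20" per cent. The rule is written for both groups with no exemption for NPO.
- **Feeding (Introduction).** Usual NG feeding is "2 hourly starting at morning and continue up to night (10 feeds/day"). The same section says that a dislodged tube interrupts feeding and so raises the risk of hypoglycemia.
- **Why hypoglycemia matters (Rationale; Outcome variables).** "Episodes of hypoglycemia may cause further neurological deterioration in acute stroke patients". "The primary safety outcome will be the frequency of hypoglycemic events (BG <3.9 mmol/L").
- **Other cover (Study Procedure).** Nurses monitor BG as routine care, an investigator visits daily and adjusts the dose on the previous day's profile, and investigators can be telephoned at any hour. None of these sets a night measurement.

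**The concern.** The outcome is defined by a measured value, so it can be recorded only when someone measures. The plan names interrupted feeding as a risk state and keeps basal insulin running in it. It then leaves the BG schedule as it was for fed patients, or, read strictly, with no schedule at all, because the checks hang on boluses that the NPO regimen does not list.

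Two things are at stake. The first is patient safety: a low value overnight may not be seen until morning, and the dose reduction cannot act before it is seen. The second is ascertainment: an episode that begins and ends between 6 pm and 6 am, with no unscheduled check, leaves no trace in the primary safety outcome.

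**Working it through.** The plan gives no figure for detection, NPO frequency or episode length, so there is nothing of its own to reproduce here. Its one computed design figure, 50 per group, does not bear on this point.

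**Inputs from the plan.** Scheduled checks at 6, 12 and 18 h (the generous reading, in which the clock times survive without a bolus); threshold 3.9 mmol/L; 50 patients per arm; planned χ² test for categorical variables.

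**Assumptions.** Episode onset uniform between 6 pm and 6 am; length d hours; no unscheduled check.

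**Step 1: the gap.** From 18 h to 6 h is 12 of 24 hours without a scheduled value. The longest possible delay to the next scheduled check is 12 h.

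**Step 2: detection under the plan.** Only the 6 am check can fall inside an overnight episode, so P(seen) = d/12 for d ≤ 12.

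**Step 3: detection with 10 pm and 2 am added.** The night then has three checks 4 h apart, so P(seen) = min(1, 3d/12).

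| d | Plan: seen | Plan: missed | With added checks: seen |
|---|---|---|---|
| 1 h | 1/12 = 8% | 92% | 3/12 = 25% |
| 2 h | 2/12 = 17% | 83% | 6/12 = 50% |
| 3 h | 3/12 = 25% | 75% | 9/12 = 75% |
| 4 h | 4/12 = 33% | 67% | 12/12 = 100% |
| 6 h | 6/12 = 50% | 50% | 100% |

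**Step 4: sensitivity.**
- *Later onset.* If all onsets fall between midnight and 6 am, P(seen) under the plan is d/6. The missed share is then 67% at 2 h, 50% at 3 h and 33% at 4 h.
- *Unscheduled checks.* Let these catch a share s of the episodes otherwise missed. More than half stay uncounted while (1 − s)(1 − d/12) > 0.5. At 2 h this means s < 1 − 0.5/0.833 = 40%; at 3 h, s < 1 − 0.5/0.75 = 33%.

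**Step 5: effect on the arm comparison (illustrative rates, one episode per patient).**
- *Equal detection.* A true 6/50 versus 2/50 is 12% − 4% = 8 points. At 17% to 33% detection it is recorded as 8 × 0.167 = 1.3 to 8 × 0.333 = 2.7 points. The ratio stays at 3 to 1.
- *Unequal detection.* Take a true 6/50 in each arm, with 2 h episodes in one and 4 h in the other. The recorded rates are 12% × 0.167 = 2% and 12% × 0.333 = 4%. A true difference of zero becomes 2 points.
- *Power.* With full detection, 6/50 versus 2/50 has pooled proportion 8/100 = 0.08 and standard error √(0.08 × 0.92 × 2/50) = 0.054. So z = 0.08/0.054 = 1.47, p = 0.14.

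**The case against.** **The gap is not particular to NPO patients.** This stands. Every patient lacks a scheduled value from 6 pm to 6 am. The NPO rule also omits the scheduled boluses and lowers or drops NPH, so insulin exposure may fall. A fed patient has a 6 pm bolus and full basal insulin and, if the first of ten feeds is at 6 am (an assumption), no feed from about midnight. A reader might infer that NPO nights carry more hypoglycemia than fed nights; the documents give no rates that would show it. The narrower point is that the plan names interrupted feeding as a risk, writes a special insulin rule for it, and adds no check.

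**The missed share depends on what is assumed.** This stands too. An untreated episode under continuing basal insulin may last until 6 am and be counted. At 6 h the missed share is 50%, and 4 h episodes starting after midnight are missed only 33% of the time. A reader might infer that most overnight episodes will be lost. That follows only for short episodes with few unscheduled checks, and the documents give neither their length nor their timing.

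**Nurses can measure at any time and investigators are on call.** Partly right. Neither the outcome nor the 20% rule is limited to scheduled values, so an unscheduled BG below 3.9 mmol/L counts and triggers the reduction. But someone must first suspect a problem, and the trial is open-label.

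**The comparison need not be pushed towards no difference.** This stands. A reader might infer that under-detection always hides an arm difference. The absolute difference is sure to shrink only if detection is equal in both arms. The plan itself says the insulins differ in pharmacokinetics, so episode length or timing may differ. Nor would full detection make the 6/50 versus 2/50 illustration significant.

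**Conclusion.** The point holds as a modest, concrete weakness in patient safety and in ascertainment. Followed as written, the plan leaves an unfed patient on basal insulin with no scheduled BG for 12 hours. Detection and the 20% reduction may be delayed by up to that long, and episodes that resolve before 6 am without an unscheduled check are not counted.

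The size is conditional: 67% to 83% of 2 to 4 h overnight episodes missed, given uniform onset and no unscheduled check, and less with longer episodes, later onset or active night checking. The total number of missed events cannot be estimated, because the plan gives no frequency or duration of NPO periods. The direction of any effect on the arm comparison is unknown.

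A reader might also take the different basal handling in the two arms (glargine unchanged, NPH reduced or optional) as an error. It is part of the regimens being compared, and nothing in the documents makes it one. The missing NPH dose and trigger need clarification only.

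**What to change.** Add to Study Procedure:

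> While a patient is NPO, BG is measured at 6 am, 12 pm, 6 pm, 10 pm and 2 am in both arms, whether or not a bolus is given, and every value is recorded. Mean daily BG uses only the 6 am, 12 pm and 6 pm values. Hypoglycemia is reported using all values and, as a sensitivity analysis, using only the three common times, because NPO status arises after randomization.

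This secures the daytime checks, cuts the longest overnight gap from 12 h to 4 h, and leaves the sampling times for the primary efficacy measure unchanged. Basal dosing stays as planned. As a clarification, state the NPH dose and the trigger for giving it.

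**Cost.** Two extra finger-pricks per NPO night, by nurses who already measure BG. Assuming 100 patients × 7 days = 700 patient-days, of which 5% to 20% are NPO, that is 35 to 140 nights × 2 = 70 to 280 strips, on top of 700 × 3 = 2,100 (3% to 13%). No extra patients or visits are needed.

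**Downside.** Detection becomes more intensive on NPO nights than on fed nights. If NPO time differs between arms, so does detection; the sensitivity analysis on the three common times is there for that reason. Fed nights keep their 12 h gap.

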- To evaluate the efficacy and safety of human insulin (regular insulin and intermediate acting NPH insulin)
- To assess the efficacy and safety of insulin analog (basal insulin glargine and rapid acting insulin aspart)
- To compare the efficacy and safety of two insulin regimen
- To evaluate the socio-demographic and clinical characteristics of the patients included in two treatment arms

METHODOLOGY:

Type of study: Single-center, open-label, randomized trial

Place of Study: Department of Neurology, National Institute of Neurosciences & Hospital, Dhaka.

Study Period: February to June, 2021

Study population: Patients admitted in the Department of Neurology with acute stroke and hyperglycemia

Sample Size:

Sample size was calculated according to following formula for non-inferiority trial (17):

$$N = 2 \times \left(\frac{Z_{1-\alpha} + Z_{1-\beta}}{\delta_0} \right)^2 \times S^2$$

Here, N= sample size per group

$$\alpha = 0.05$$

$$\beta = 0.20$$

δ_0 = a clinically acceptable margin (assumed as 3 mmol/L of blood glucose)

S² = Pooled standard deviation of both comparison group = 8

So,

$$N_{\text{non-inferiority}} = 2 \times \left(\frac{1.645 + 0.845}{3} \right)^2 \times 6^2 = 50$$

As a result, 50 patients will be randomly assigned to two treatment groups (50 human insulin regimen, 50 analog insulin regimen).

Inclusion criteria

- Patients admitted to adult neurology ward with acute stroke with
- Patients having hyperglycemia (capillary blood glucose ≥ 10 mmol/L in 2 or more occasions or having history of treatment for DM)
- Patients with age of 18-80 years of both sexes
- Patients or their attendants giving consent to take part in the study

Exclusion Criteria

- Patients with hyperglycemic emergencies (hyperglycemic hyperosmolar state or diabetic ketoacidosis)
- Pregnant patients
- Those not giving consent to participate in the study

Study Procedure

Patients will be randomly assigned to receive either a human insulin regimen (starting with regular insulin three times a day with NPH insulin twice a day) or analog insulin regimen (basal insulin glargine once daily and insulin aspart three times a day) following a computer-generated randomization table. All oral antidiabetic drugs will be discontinued on admission.

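### Participants given an incorrect insulin regimen after randomisation are dropped from every outcome, and no as-randomised analysis is planned

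*Combined protocol and SAP*

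**What the plan says.** All places are in the Methodology part (Section-C) of the combined protocol and SAP unless stated.

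- **Protocol deviation and protocol violation.** Deviations and violations are separated. For the first: "Deviation to protocol will be recorded and reported to ethical committee as soon as possible". Violations are failure to obtain written consent and two further items: "use of incorrect insulin regimen, not fulfilling inclusion and exclusion criteria will be regarded as protocol violation". For all three: "In case of protocol violation, the data of related participant will be discarded".
- **Type of study.** "Single-center, open-label, randomized trial".
- **Sample Size.** "Sample size was calculated according to following formula for non-inferiority trial". It uses 50 per arm, a margin of 3 mmol/L and a one-sided 0.05 level (Z = 1.645).
- **Study Procedure.** After a daily visit, "insulin dose will be adjusted according to glucose profile of previous day". The patients are described as mostly having "severe stroke with case fatality rate around 20" per cent.
- **Outcome variables.** The primary efficacy outcome is mean daily glucose over the hospital stay. "The primary safety outcome will be the frequency of hypoglycemic events (BG <3.9 mmol/L"). Mortality is secondary.
- **Statistical analysis**, and the Abstract for the IRB/Ethical Committee. These give the t-test or Mann-Whitney test, the chi-squared test, two-tailed probabilities and p ≤ 0.05. Neither names an as-randomised, per-protocol or safety population.

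**The concern.** The three violations are not alike. Not using data where consent is absent is proper. Excluding a patient who was ineligible on facts fixed before randomisation need not bias anything, if the judgement is made without knowledge of arm or outcome. A wrong regimen is different: it happens after assignment, so removing those patients can undo the balance that randomisation created.

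Such removals could plausibly relate to outcome and differ by arm. Treatment is open, and doses follow the previous day's glucose, so a poorly controlled patient has more changes and more chances for error. The human arm has five scheduled insulin doses a day (three regular, two NPH) and the analog arm four (one glargine, three aspart). The protocol's Justification describes analogs as expensive and of limited availability. None of this proves a difference, but nothing in the plan guards against one.

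The rule also reaches safety. If a regimen error leads to hypoglycaemia, that patient's events leave the primary safety outcome. A death in such a patient leaves the mortality comparison.

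**Working it through.** **1. The plan's own figure.** N = 2 × ((1.645 + 0.845)/3)² × 6² = 49.6, so 50 per arm, as stated. This needs SD 6. The text gives 8 under the label S², so I also show SD 8 and variance 8 (SD 2.83). The calculation contains no allowance for discarded patients.

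**2. Bias formula.** Let p be the share discarded in an arm and d the mean glucose of discarded minus retained patients in that arm. The full-arm mean equals the retained mean plus p×d, so discarding lowers that arm's mean by p×d. With A the arm under test and higher glucose worse, the comparison moves in A's favour by

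b = pA×dA − pB×dB.

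This is zero if both gaps are zero, or if the products are equal. For example, 5% with gap 6 and 10% with gap 3 give 0.30 − 0.30 = 0.

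**3. Error rates.** Every p and d below is an assumption, because the documents give none. I use the normal approximation with SE = SD × √(1/nA + 1/nB), n after discards.
- False non-inferiority when the as-randomised difference equals the margin: 1 − Φ(1.645 − b/SE).
- Two-tailed 0.05 test with no true difference: 1 − Φ(1.96 − b/SE) + Φ(−1.96 − b/SE).

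Example (15% vs 5%, gap 4 in both arms, SD 6): b = 0.60 − 0.20 = 0.40; SE = 6 × √(1/42.5 + 1/47.5) = 1.267; b/SE = 0.316. False non-inferiority = 1 − Φ(1.329) = 9.2%. Two-tailed error = 1 − Φ(1.644) + Φ(−2.276), about 6.2%.

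| Discarded A / B | Gap A / B | b | False non-inferiority: SD 6 / SD 8 / variance 8 | Two-tailed error: SD 6 / SD 8 / variance 8 |
|---|---|---|---|---|
| 10% / 10% | 2 / 2 | 0 | 5% / 5% / 5% | 5% / 5% / 5% |
| 10% / 5% | 2 / 2 | 0.1 | 5.9% / 5.6% / 7.0% | 5.1% / 5.0% / 5.3% |
| 15% / 5% | 4 / 4 | 0.4 | 9.2% / 8.0% / 16.5% | 6.2% / 5.6% / 10.3% |
| 10% / 10% | 4 / 0 | 0.4 | 9.2% / 8.0% / 16.5% | 6.2% / 5.6% / 10.3% |
| 5% / 15% | 4 / 4 | −0.4 | 2.5% / 3.0% / 1.0% | 6.2% / 5.6% / 10.3% |

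**4. Power without bias.** Φ(3/(SD × √(2/n)) − 1.645) at n = 50, 45 and 40 (0%, 10%, 20% discarded): 80%, 77%, 72% at SD 6; 59%, 55%, 51% at SD 8; above 99% at variance 8.

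**5. Events lost.** If trial mortality matched the quoted 20%, 100 patients would have 20 deaths. Discarding 10% of patients, unrelated to death, would remove about 2 of them.

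**6. The as-randomised analysis has its own weakness.** Suppose 10% and 5% received the other arm's insulin throughout (assumption). A true regimen difference of 3 becomes 3 × (1 − 0.10 − 0.05) = 2.55, a shift of 0.45. With 50 per arm, false non-inferiority for the regimen difference is 1 − Φ(1.645 − 0.45/SE) = 10.2% at SD 6, 8.6% at SD 8 and 19.8% at variance 8.

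**7. Power if both analyses must show non-inferiority.** Taking the two test statistics as bivariate normal with correlation √(n/50) and no bias, power falls from 80% to about 74% and 70% with 10% and 20% discarded at SD 6, and from 59% to 52% and 47% at SD 8.

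**The case against.** The strongest reply has four parts.

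- **Scope.** Each regimen is described by insulin types and daily injections, and deviations are only recorded. An incorrect regimen may therefore mean wrong-arm insulin, not a slip in titration or a supplemental dose. A reader might infer that any dosing slip removes the patient; the text does not say so, and giving the planned supplemental or nil-by-mouth insulin is not a violation. What stands is that the boundary is undefined and no one is named to judge it. Even wrong-arm insulin is a post-randomisation event, so the point survives the narrow reading. That reading does weaken the link to the previous day's glucose, because the cause may be an allocation or supply error.
- **Size.** No violation rate is given, and daily investigator visits with round-the-clock telephone cover may keep errors few. Under the two-tailed test actually planned, the illustrated error is only 5.1% to 6.2% at SD 6. The larger figures belong to a non-inferiority test that the Sample Size section implies but the Statistical analysis section does not set out. This stands.
- **Per-protocol suits non-inferiority.** It is useful beside an as-randomised analysis, which can be diluted by a similar amount (step 6). Here there is nothing to set beside it.
- **Deletion.** A reader might take discarded to mean erased. The documents do not say so, and violations must be reported to the ethics committee. If the word means only excluded from analysis, an as-randomised check remains possible but is not planned.

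**Conclusion.** The rule is wrong as written. It is an explicit post-randomisation exclusion in an open-label trial, it applies to both primary outcomes and to mortality, and it is the plan's only rule on which participants are analysed. It is not the only analysis rule, since tests, sidedness and significance level are given.

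A reader might go further and infer that the result will be biased, that one arm is favoured, or that unequal discard rates alone are enough. The documents support none of these. Bias requires unequal products of rate and gap, and neither quantity is given, so size and direction are unknown. The bias of 0.4 mmol/L rests wholly on assumed rates and gaps; with milder assumptions (10% against 5%, gap 2) the effect is slight.

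The loss of safety events does not depend on any assumed glucose gap: whatever hypoglycaemia or death occurs in a discarded patient is not counted. The example of 2 deaths in 20 shows lost information, not bias.

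**What to change.** Replace the discard sentence with rules to this effect:

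- **Primary analysis:** all randomised participants with valid consent, in their assigned arm. The only other permitted exclusion is ineligibility on facts fixed before randomisation, judged without knowledge of arm or outcome.
- **Data:** keep everything collected on consenting participants, including hypoglycaemia and deaths, and analyse safety on it.
- **Violations:** state in advance which regimen errors count as violations and which as deviations, and report violations by arm with reasons.
- **Supporting analysis:** a per-protocol analysis that excludes the predefined violations, because the as-randomised estimate can be diluted toward non-inferiority.

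The plan should also say how a randomised patient with no glucose reading after assignment is handled.

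Requiring both analyses to agree before non-inferiority is concluded is optional. If it is adopted, the power cost in step 7 should be stated.

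The cost is protocol wording and one extra analysis of data already collected. The downside is possible dilution of the as-randomised estimate. No dose or clinical rule changes.
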